Protocol Component	Description under target trial	Description under Emulation
Eligibility Criteria	Adult inpatients receiving B-lactam therapy for culture confirmed monomicrobial invasive GAS between who can be randomized within 72h of index culture	Adult inpatients receiving B-lactam therapy for culture confirmed monomicrobial invasive GAS between the years 2015-2021 in the PINC AI™ dataset who receive anti-toxin within 3 days of index culture.
Treatment strategies	B-lactam therapy as primary therapy for GAS started within (+/-) 3 days of index GAS culture and continued for a minimum of 3 consecutive days. Adjunctive anti-toxin (clindamycin vs. linezolid) therapy started within (+) 3 days of culture.	Same as target trial.
Assignment procedures	
Patients will be randomly assigned within 3 days of culture (grace period) to clindamycin vs. linezolid. Investigators and patients and will be aware of the strategy to which they have been assigned (pragmatic, unblinded, open-label non-inferiority).
 
Switching between linezolid and clindamycin will not be permitted under the protocol.
	
Patients will be assigned to the anti-toxin therapy compatible with their observed treatment. Difference in baseline characteristics and confounding by indication will be addressed through the creation of a propensity weighted cohort.
 
Those who received both agents within the eligibility period will be excluded.

Follow up period	Starts at time of randomization (anti-toxin initiation) and ends at death, discharge to hospice, loss to follow up or 90 days, whichever occurs earliest.	Starts at time of anti-toxin initiation and ends at death, discharge to hospice or discharge from the hospital to home or facility or administrative censorship on Jan 31 st 2022.
Outcome	
Primary outcome: Time to all-cause mortality (or discharge to hospice) censored at 90 days.
 
Secondary outcome: infection attributable 90-day mortality, all-cause in-hospital mortality, 90-day disease reoccurrence, length of stay following anti-toxin administration among survivors, occurrence of CDI
	
Primary outcome: All-cause in-hospital mortality (or discharge to hospice)/ time to death (days).
 
Secondary outcome: Length of stay following anti-toxin administration among survivors, occurrence of CDI requiring treatment following anti-toxin administration.

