requiring treatment following anti-toxin administration up to 90 days, occurrence of serotonin surge syndrome while on therapy.

Causal contrast of interest	Intention-to-treat effect; per-protocol effect.	Observational analog to Intention-to-treat effect and per-protocol effect.
Analysis plan	Intention-to-treat and per protocol effects estimated via comparison of adjusted 90 day in-hospital mortality risk assigned to each treatment strategy.	
Intention-to-treat and per protocol effects estimated via comparison of adjusted in-hospital mortality risk assigned to each treatment strategy.
 
To account for confounding by indication a propensity score (PS) will be generated based on the probability of receiving linezolid using the patient and center level variables selected a priori based on clinical judgment, . Overlap weighting on a propensity-score between the two groups will be performed with downstream adjustment for ICU stay , shock and debridement/source control.

Abbreviations: CDI: Clostridioides difficile infection; GAS: Group A streptococcus.

The study was designed in accordance with the trial emulation approach described by Hernán and Robins¹⁹. The study aims to emulate a hypothetical target pragmatic multi-center, non-blinded trial.

Eligibility

Adult inpatients patients (≥ 18 y of age) with culture confirmed proven or probable (see below) invasive monomicrobial GAS in the PINC AI™ database between 2015-2021 who receive a β -lactam for a minimum of 3 days within 3 days of culture will be eligible for inclusion in the emulated trial. Patient will be included if they then receive anti-toxin therapy within 3 days of culture being drawn, as long as B-lactam therapy has been initiated prior or on the same day as antitoxin therapy.

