Proven and probable invasive GAS definitions will be adapted from the CDC ABCs case definition (<https://www.cdc.gov/abcs/methodology/case-def-ascertain.html>) using a previously used algorithm compatible with EHR data which incorporates ICD-codes³. Proven invasive GAS infection will be defined as GAS isolated from a normally sterile site, such as blood, cerebrospinal fluid, pleural fluid, peritoneal fluid, pericardial fluid, bone, joint/synovial fluid, or internal body site (e.g., lymph node, brain) OR GAS isolated from a wound culture and accompanied by necrotizing fasciitis or streptococcal toxic shock syndrome. Probable invasive GAS infection is defined as the isolation of GAS from a non-sterile site in patients with either an ICD-10 code that matches the clinical infection syndrome (eg ICD-10 for lower respiratory infection and BAL culture with GAS) or a non-specific streptococcal infection code. These include lower respiratory, musculoskeletal, genitourinary and/or skin and soft tissue samples as well other miscellaneous deep-seated infections (eg retropharyngeal abscess). Previously identified ICD-9 codes³ will be cross walked to ICD-10 codes manually with additional manual de-novo search for compatible ICD-10 codes. Final codes and culture site classification will be adjudicated by two infectious diseases clinicians.

Inclusion Criteria

- Adult inpatients patients (≥ 18 y of age)
- Monomicrobial Group A streptococcus invasive infection
- Primary therapy with a B-lactam agent (initiated before or on same day as adjunctive anti-toxin therapy)

Exclusion Criteria

Patient will be excluded if they have any of the following :

- Patients with a polymicrobial GAS culture
- Patients who allocated to the linezolid arm but have a documented linezolid resistant isolate
- Patient with concomitant MSSA/MRSA invasive infection (+/- seven days of index GAS eligibility culture)
- Patients who receive both anti-toxin agents (violation of protocol)
- Patient who don't complete at least 3 days of B-lactam (violation of protocol)

Primary Outcome measure:

in-hospital mortality defined as death during hospitalization or discharge to hospice.

Secondary outcome measures:

- Length of stay among survivors

- *Clostridioides difficile* infection

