Statistical analysis will be performed with R using Rstudio V2022.12.0.353 (R Foundation for Statistical Computing, Vienna, Austria). The reporting of the study will be in line with Strengthening the Reporting of Observational Studies in Epidemiology (STROBE) reporting guidelines²⁰

Sensitivity analysis

The following sensitivity analysis will be performed:

- Analysis of patients with proven GAS only (excluding those with probable GAS)
- Analysis where hospital as a random effect is not included
- An analysis which includes those who receive anti-toxin +/-3 days of index therapy to capture those treated empirically prior to culture results.
- An analysis without PS weighting and only downstream logistical regression (as would be done in a classical observational study).
- An analysis utilizing cloning methodology to account for potential immortal time bias²¹

Subgroup Analysis

We will use similar methods as for the primary analysis to assess the impact of allocation to either treatment group on the following prespecified subgroups

- Patients with NSTI or TSST
- Patients with pressor dependent shock
- Patients admitted to the ICU within one day (+/-) of index GA eligibility culture
- Excluding patients with who received clindamycin that had a clindamycin non-susceptible isolates (defined as resistant or intermediate or a positive D-test)
- Excluding patients with who received clindamycin that had a clindamycin non-susceptible isolates or had clindamycin antimicrobial susceptibility testing missing
- Stratified by days of anti-toxin therapy (>1, >2, >3 days)

Missing Data Plan

Less than 5% missingness across key variables is expected

References

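### Arm comparisons within groups cut by days of anti-toxin received condition on events after time zero, which baseline weighting does not correct (subgroup results only; minor)

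*Combined protocol and SAP*

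**What the plan says.** The Subgroup Analysis section introduces its list with "We will use similar methods as for the primary analysis to assess the impact of allocation to either treatment group". The last item on that list is "Stratified by days of anti-toxin therapy (>1, >2, >3 days".

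Other parts of the combined protocol and SAP bear on how that item can be read:

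- **Time zero.** Table 1, follow-up under the emulation: "Starts at time of anti-toxin initiation and ends at death, discharge to hospice or discharge from the hospital to home or facility".
- **Treatment strategies.** Table 1 requires the B-lactam to be "started within (+/-) 3 days of index GAS culture and continued for a minimum of 3 consecutive days". For the anti-toxin it gives only a start window: "Adjunctive anti-toxin (clindamycin vs. linezolid) therapy started within (+) 3 days of culture".
- **Estimands.** Table 1 names an "Observational analog to Intention-to-treat effect and per-protocol effect".
- **Exclusions.** The list includes "Patient who don't complete at least 3 days of B-lactam (violation of protocol" and "Patients who allocated to the linezolid arm but have a documented linezolid resistant isolate". It also removes patients who received both anti-toxin agents; the assignment row of Table 1 limits that exclusion to the eligibility period.
- **Confounding control.** The Statistical Analysis Plan section builds the propensity score from variables linked to starting linezolid rather than clindamycin and to mortality, then applies overlap weights. It mentions no predictors of stopping.
- **Cloning.** The Sensitivity analysis section lists a cloning analysis for immortal time bias, without linking it to the duration groups.

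**The concern.** Days of anti-toxin received are not a baseline characteristic. To pass the cut at more than k days, a patient must survive and remain on the drug beyond the day on which follow-up began. If days are counted from inpatient records (an assumption), discharge home before the cut also removes a patient, and that patient is a survivor under the in-hospital outcome.

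Weights that balance the arms at initiation do not keep them balanced among those who continue. If the reasons for stopping, or the timing of early deaths, differ between the drugs and are tied to prognosis, the arms within a duration group differ in prognosis even when neither drug affects mortality. A result among patients treated for more than 3 days, reported as an effect of allocation, could then reflect who stopped.

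The groups are not a per-protocol analysis either. Table 1 specifies no anti-toxin duration, so there is no duration strategy to which a patient could adhere.

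**Working it through.** The documents give no figure for the duration groups, so there is none to reproduce. Three checks follow.

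**1. How much extra survival does each cut require?** The 3-day B-lactam exclusion already requires some survival in the whole cohort. Count calendar days, with the first B-lactam day as day 1 of 3 and anti-toxin days consecutive. Let L be the number of days by which the B-lactam start precedes the anti-toxin start. Table 1 allows the B-lactam from culture day −3 and the anti-toxin up to culture day +3, and Eligibility requires the B-lactam on or before the anti-toxin day. L therefore runs from 0 to 6.

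Completing the B-lactam requires survival for max(0, 2 − L) days past anti-toxin start. Passing the cut >k requires k days. Added days = max(0, k − max(0, 2 − L)).

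| L | >1 | >2 | >3 |
|---|---|---|---|
| 0 | 0 | 0 | 1 |
| 1 | 0 | 1 | 2 |
| 2 or more | 1 | 2 | 3 |

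The exclusion thus absorbs part of the selection on death, and at the first two cuts all of it when both drugs start on the same day. It does nothing about selection on continuing the anti-toxin, which applies at every cut.

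**2. How large could selection on continuation be?** The 6.5% mortality in both arms comes from the Power calculation section. The rest is assumed: no drug effect, no deaths before the cut, stopping itself harmless and not predicted by baseline covariates. Let p = 0.065, s = share of eventual survivors stopping before the cut, and d = share of patients who later die stopping before it.

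Group mortality = p(1 − d) / [p(1 − d) + (1 − p)(1 − s)]

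Compare s = 0.10 in one arm with s = 0.30 in the other:

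- **d = 0 (extreme case):** 0.065/0.9065 = 7.17% against 0.065/0.7195 = 9.03%; difference 1.86 points.
- **d = s/2:** 0.06175/0.90325 = 6.84% against 0.05525/0.70975 = 7.78%; difference about 0.9 points.
- **d = s (unrelated to outcome):** 6.5% in both arms; difference 0.

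With 10% against 20% stopping, the first two cases give 0.065/0.813 = 8.00% (difference 0.8 points) and 0.0585/0.8065 = 7.25% (difference 0.4 points). With equal stopping in both arms, every case gives 0. The sign depends on which arm stops more.

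**3. Scale.** The planned 207 linezolid and 828 clindamycin patients, less the 10% dropout allowance, leave 186.3 and 745.2. The 95% half-width for a difference at 6.5% is 1.96 × √[0.065 × 0.935 × (1/186.3 + 1/745.2)] = 3.96 points, before any precision lost to weighting. Duration groups can be no larger than the cohort, so their intervals will be at least about this wide. Expected linezolid deaths: 186.3 × 0.065 = 12.1.

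**The case against.** The strongest reply is that nothing in the documents shows that stopping or early death differs by arm. Without such a difference the contrast is unbiased, although each group's absolute mortality is still that of a selected group. That stands, and it is why no size or direction can be claimed.

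A reader might infer an arm-specific mechanism from the handling of resistance: linezolid-resistant isolates leave the linezolid arm, while clindamycin non-susceptible isolates stay in the clindamycin arm except in two separate subgroup analyses. It is tempting to say that a susceptibility result prompts stopping in one arm only. The documents do not support so firm a statement. Under the Exclusion Criteria as written, a patient switched from clindamycin to linezolid leaves the cohort. What remains is stopping without replacement, plus later switches if the narrower wording in Table 1 governs. Keeping these isolates shows that such patients can be in the cohort, not that they stop early. It is a possible route of unknown frequency.

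A reader might also take it that one-day patients are lost from these analyses. They pass none of the three cuts, but the plan does not say whether each cut is also analysed against its complement. This is a point to clarify, not an established exclusion.

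It is fair to add that the illustrated bias lies below the sampling uncertainty, and that the plan claims an effect of allocation within groups, not an effect of duration. Neither removes the problem: selection bias does not shrink with sample size, a confidence interval does not reveal it, and the within-group effect of allocation is exactly the claim these groups cannot carry.

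**Conclusion.** The point holds for the duration groups only, and it is minor. Membership is fixed after time zero, the planned baseline weighting does not correct for that, and no other method in the plan is assigned to these groups. Whether the arm contrast is actually biased depends on differential, prognosis-related stopping or early death, which the documents neither show nor rule out.

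The illustrated range of 0 to 1.9 points rests on assumed stopping rates. The upper end needs both a 10% against 30% split and no stopping at all among patients who later die. It should not be read as an estimate.

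A reader might extend this to the main result. The documents do not support that: the primary comparison does not use the duration cuts.

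**What to change.** State in the Subgroup Analysis section that the groups by days of anti-toxin are descriptive, with no causal comparison between arms, and say how one-day patients are handled (whether each cut is also shown against its complement). This costs a sentence or so in the SAP and no new data. The price is giving up the claim of an effect of allocation within duration groups.

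If a duration-specific effect is wanted, define sustained-duration strategies in Table 1 and compare them by clone-censor-weight from anti-toxin initiation. Deaths before the threshold should be counted, and predictors of stopping measured after initiation should enter the weights. This needs more programming and day-stamped data on stopping and its predictors. The weights may be unstable with about 186 linezolid patients and about 12 deaths. A landmark analysis alone would make the question clearer but would leave the selection on continuation in place.
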